4.6.7. Other variables and/or parameters

Fibrosis Score is collected at baseline and End of Study (or Early Termination). A shift table for Metavir fibrosis score showing baseline score and End of Study (or Early Termination) score will be provided for each arm, overall and by baseline HBeAg status.

A listing of participants who went above and stayed above >=90 IU/mL HBV DNA will be presented. All visits will be presented for these participants.

A listing showing (quantitative) values of HBeAg at Baseline & Day 1 will be presented for subjects who are anti-HBeAg positive at baseline. A listing showing (quantitative) values of HBsAg at Baseline & Day 1 will be presented for subjects who are anti-HBsAg positive (i.e. HBs Antibody >=11.5 IU/L) at baseline.

4.7. Interim Analyses

Details of interim analyses are provided in separate Interim Analysis Reporting and Analysis Plans.

4.8. Changes to Protocol Defined Analyses

Changes from the originally planned statistical analysis specified in the protocol are detailed in Table 9.

Table 9 Changes to Protocol Defined Analysis Plan

Protocol Defined Analysis	SAP Defined Analysis	Rationale for Changes
NA - addition	SAP Section 4.2.4.3: Addition of a supplementary estimand that uses a principal stratum strategy to deal with protocol deviations	A number of subjects in the not currently on nucleos(t)ide therapy population started nucleos(t)ide therapy on day 1 because of a misunderstanding of the protocol. In the main estimand these participants will be treated as failures on day 1. However, as these patients never had the chance to respond because of an

Protocol Defined Analysis	SAP Defined Analysis	Rationale for Changes
		operational error, this estimand will be used to counter the main estimand,
NA - addition	SAP Section 4.2.4.4: Addition of a supplementary estimand to assess efficacy using a modified definition of SVR	There are a number of subjects with single lab values that are aberrant in terms of the individual's overall trajectory of response. There is some evidence that the aberrant values have occurred because of an unresolvable error at the site/lab. As the issues cannot be resolved in the data, this estimand will be used to support the primary objective.

5. SAMPLE SIZE DETERMINATION

Approximately 440 participants are planned to be randomly assigned to study intervention.

For each population, there will be approximately 66 participants assigned in each of the first three arms. There will be approximately 22 participants assigned in the fourth arm.

It is assumed that the number of responders follows a Binomial distribution, with a weakly informative prior (Beta (0.5, 0.5)) for the true response rate. The precision for a range of response rates with 95% credible intervals are shown in Table 10.

Table 10 95% Credible Interval of Response Rate by Sample Size

Sample size per arm	Number of responders	Response rate	95% credible interval*
22	2	9%	1% – 23%
	3	14%	3% - 30%
	4	18%	5% - 36%
	5	23%	8% - 41%
	6	27%	11% - 46%
66	6	9%	3% - 17%
	9	14%	6% - 23%
	12	18%	10% - 28%
	15	23%	13% - 33%
	18	27%	17% - 38%

^{*95%} highest posterior density interval

The lower bounds of 95% credible intervals will exclude the historical placebo response rate of 3% if observed response rate is greater than or equal to 14% in arms 1-3 or 18% in arm 4.

The posterior probabilities that the true sustained virologic response rate is greater than a range of response rates will be calculated from the implied Beta posterior, given the actual number of responders observed.

The operating characteristics based on at least 75% posterior confidence that the true rate exceeds a threshold of interest, are shown in Table 11, for various sample sizes, and true cure rates. The operating characteristics shown are based on a Bayesian model without consideration of baseline analysis stratification factors and expected to be similar to operating characteristics from the hierarchical model defined in Section 4.2.2.

Table 11 End of Study Operating Characteristics by Sample Size

Criterion	Sample Minimum size per number (%) arm of		Probabili	ty of Meeting Assun	Criterion Und	er Various
		responders required to meet Criterion	True Resp Rate=5%	True Resp Rate=20%	True Resp Rate=25%	True Resp Rate=30%
Probability (true	22	5 (23%)	0%	46%	68%	84%
response	44	9 (20%)	0%	53%	81%	91%
rate>15%)>75%	66	12 (18%)	0%	69%	93%	99%
	88	16 (18%)	0%	71%	95%	100%
Probability (true	22	6 (27%)	0%	27%	48%	69%
response	44	11 (25%)	0%	25%	56%	81%
rate>20%)>75%	66	16 (24%)	0%	23%	60%	88%
	88	21 (24%)	0%	22%	64%	92%
Probability (true response rate>25%)>75%	22	7 (32%)	0%	13%	30%	51%
	44	13 (30%)	0%	9%	29%	58%
	66	19 (29%)	0%	6%	28%	63%
	88	25 (28%)	0%	4%	27%	67%

Note: If the true response rate is 0%, the probability of meeting each criterion is 0% for all sample sizes.

Based on these operating characteristics, for a true response rate of 20%, the proposed sample-size of n = 66 for arms 1 - 3 has ~70% probability of confirming a true response of at least 15%, and if the true rate is 30%, there is an 88% chance of confirming a true response of at least 20%.

There are no plans for sample size re-estimation.

TMF-13936631 **CONFIDENTIAL** 209668

6. SUPPORTING DOCUMENTATION

6.1. Appendix 1 Study Population Analyses

Unless otherwise specified, the study population analyses will be based on the Enrolled Analysis Set. A summary of the number of participants in each of the participant level analysis set will be provided.

A listing of subjects excluded from any population will be presented.

In this multicentre global study, enrolment will be presented by country and site.

6.1.1. Participant Disposition

A summary of the number and percentage of patients who were screened including screen failures will be provided. Reasons for failure will be included.

A summary of the number and percentage of participants who completed the study as well as those who prematurely withdrew from the study will be provided. Reasons for study withdrawal will be summarized.

A summary of study intervention status will be provided. This display will show the number and percentage of participants who completed the scheduled study intervention, or who discontinued study intervention prematurely, as well as primary reasons for discontinuation of study intervention.

Summaries of disposition, adverse events leading to withdrawal and reasons for withdrawal will be presented by Study Period, as defined in the Output and Programming Specification.

Listings of reasons for study withdrawal, screen failure and study treatment discontinuation will be provided.

6.1.2. Demographic and Baseline Characteristics

Unless otherwise stated, study population analyses will be based on the Enrolled population.

Study population analyses including analyses of participant's disposition, protocol deviations, demographic and baseline characteristics, prior and concomitant medications, nucleos(t)ide treatment starting after randomization, medical history and exposure and treatment compliance will be presented.

Demographic characteristics including sex, age, ethnicity, race, height and weight will be summarized with descriptive statistics.

Baseline characteristics including but not limited to BMI, hypertension, NSAID use, TDF/TAF containing medications use, ADV containing medications use, diabetes, eGFR, serum creatinine, urine ACR, platelets, ANC, complement C3, complement C4,

complement C5a, complement Bb, C Reactive Protein, MCP-1, c-ANCA, p-ANCA and subgroup categories listed in Section 4.6.1 will be summarized with descriptive statistics. Continuous characteristics will be presented using summary statistics (n, Mean (SD), Median, Min, Max) and may also be categorized and summarised using n (%).

Hepatitis B characteristics, as collected on the Hep B Disease Characteristics eCRF, will be summarized using descriptive statistics, and will be listed.

A table and listing of nucleos(t)ide treatment at baseline will be presented for the on stable nucleos(t)ide cohort.

6.1.3. Protocol Deviations

Important protocol deviations will be summarized.

Protocol deviations will be tracked by the study team throughout the conduct of the study. These protocol deviations will be reviewed to identify those considered as important as follows:

- Data will be reviewed prior to unblinding and freezing the database to ensure all important deviations (where possible without knowing the study intervention details) are captured and categorised in the protocol deviations dataset.
- This dataset will be the basis for the summaries of important protocol deviations.

6.1.4. Prior and Concomitant Medications

Concomitant medications will be coded using the GSK Drug dictionary. The summary of concomitant medications will be provided by ingredient, i.e., multi-ingredient medications will be summarized for each individual ingredient rather than a combination of ingredients. The summary will be created using ingredient base names, i.e., ingredients with the same base name but different salt will appear under one base name in the summary. Anatomical Therapeutic Chemical (ATC) classifications will not appear in the summary.

A prior medication is defined as any medications that is ended prior to the date of first dose of study drug.

Medications initiated after the first dose of study drug or initiated prior to the first dose of study drug and continued after the first dose of study drug will be counted as concomitant medications. A medication that cannot be determined as prior or concomitant medication due to partially or completely missing start/stop date will be counted as both prior and concomitant medication.

6.1.5. Study Intervention Compliance

A summary of overall compliance for GSK3228836 based on the exposure data will be produced. Overall compliance will be summarized using descriptive statistics as well as the categories <80%, 80%-100%, and >100%.

Compliance will be summarized both in terms of number of injections administered and total dose received during the planned on-treatment period.

Study intervention Compliance (%) = [Number of actual doses / Number of planned doses] *100.

Study dose Compliance (%) = [Actual Total Dose / Planned Total Dose] * 100

6.1.6. Additional Analyses Due to the COVID-19 Pandemic

A participant is defined as having a suspected, probable or confirmed COVID-19 infection during the study if the answer is "Confirmed", "Probable" or "Suspected" to the case diagnosis question from the COVID-19 coronavirus infection assessment eCRF. Numbers of participants with a suspected, probable or confirmed COVID-19 infection, and of COVID-19 test results will be summarized.

If a high proportion (>5% overall) of participants have a suspected, probable or confirmed COVID-19 infection, the following data displays will be produced:

- Summary of current (and/or past) medical conditions for participants with COVID-19 adverse events.
- Summary of baseline characteristics for participants with COVID-19 adverse events.

6.2. Appendix 2 Data Derivation Rules

6.2.1. Criteria for Potential Clinical Importance

Grading categories for laboratory tests are determined using the DAIDS grading system Version 2.1 [National Institute of Allergy and Infectious Diseases. Division of AIDS, 2017].

No Laboratory tests values of potential clinical importance are defined. Laboratory values outside of normal range will be summarized and listed.

6.2.2. Assessment Windows

Refer to Section 4.2.2.1 for details of visit windowing for the main efficacy estimands.

Unless otherwise specified, no windowing will be applied to unscheduled visits. Planned time relative to dosing will be used in figures, summaries, statistical analyses and calculation of any derived parameters, unless otherwise stated. Unscheduled visits will not be included in summary tables and/or figures except from determining response for primary endpoint as described in Section 4.2.2.1 and summaries over "any time on treatment" or "any visit post-baseline". Unscheduled visits will be included in listings.

Laboratory and vital signs data collected at Early Termination Visits will be assigned to assessment windows, according to the actual date.

6.2.2.1. Definitions of Assessment Windows for Early Termination Visits

Laboratory and vital signs data collected at Early Termination Visits will be assigned to assessment windows, according to the actual date.

Analysis	Parameter	Target	Analysi	s Window	Analysis
Set / Domain	(if applicable)		Beginning Timepoint	Ending Timepoint	Timepoint
Lab, Vital	Numeric				
Signs	parameters	1	1	2	Week 1 Day 1
		4	3	6	Week 1 Day 4
		8	7	9	Week 2 Day 8
		11	10	12	Week 2 Day 11
		15	13	18	Week 3
		22	19	25	Week 4
		1+7(x-1)	1+7(x-1)-3	1+7(x-1)+3	Week x
		169	166	172	OT-Week 1
		176	173	179	OT-Week 2
		190	180	203	OT-Week 4
		218	204	231	OT-Week 8
		246	232	259	OT-Week 12
		274	260	287	OT-Week 16

302	288	315	OT-Week 20
330	316	340	OT-Week 24

Notes:

- 1. Week x includes on-treatment weeks 5-24
- 2. Visit windows are to be used for windowing of Early Termination visits only

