Pregnancy test (women of child bearing potential)	Х		Х	X	X	Х	Х	Х	Х
Hematology ² [includes platelet count and WBC]	Х	Х	Х	Х	Х	Х	Х	Х	Х
PT, INR, aPTT	Х		Х		Х	Х	Х	Х	Х
Chemistry	Х	Х	Х	Х	Х	Х	Х	Х	Х
Urinalysis	Х	Х	Х	Х	Х	Х	Х	Х	Х
Urine ACR	Х	Х	Х	Х	Х	Х	Х	Х	Х
HBsAg and HBV DNA	Х	Х	Х	Х	Х	Х	Х	Х	Х
Anti- HBsAg	Х	Х	Х	Х	Х	Х	Х	Х	Х
Anti- HBeAg	Х	Х	Х	Х	Х	Х	Х	Х	Х
HBeAg (only for participants HBeAg positive at screening)	Х	Х	Х	Х	Х	Х	Х	Х	Х
HBV RNA, HBcrAg, and Sequencing (HBV Genotype/phenotype; HBV DNA and/or RNA)	Х		Х		X		Х	Х	Х
Complement C3, Complement C4, hs-CRP, MCP-1		Х	Х	Х	Х	Х	Х	Х	Х

Assessments ¹	OT-Day 1	OT-Day 8	OT-Day 22	OT-Day 50	OT-Day 78	OT-Day 106	OT-Day 134	OT-Day 162	Early Termination
Window	±3 E	ays			±10	Days			
	OT- W1	OT-W2	OT-W4	OT-W8	OT-W12	OT-W16	OT-W20	OT-W24	
Complement C5a, Complement factor Bb		Х	Х	Х	Х	Х	Х	Х	Х
ANCA, Ang II	Х		Х	Х	Х	Х	Х	Х	Х
PK	Х	Х	X	X	X	Х	Х	Х	Х
PBMC Collection for immunophenotyping ³	Х				Х			Х	Х
Soluble Protein (immunology)	Х		Х		Х		Х	Х	Х
PAXGene RNA for expression analysis in whole blood	Х				Х			Х	Х
APRI/Fibrosure								Х	Х
Archived Samples [serum; plasma]	Х	Х	Х	Х	Х	Х	Х	Х	Х

- 1. In selected countries/sites, participants will have the option to use a centralised home nursing provider. Only selected visits will have the option to be performed as a home visit, these will include drug administration, blood draws, participant assessments and data collection. The full specifications of the home nursing services will be outlined in the SRM.
- 2. Hematology- platelet count analyzed at local laboratory is **optional** during the off-treatment period; hematology samples to be collected for central laboratory assessments (required; if local lab is being drawn, in parallel with local lab sample).
- 3. Only for selected sites able to transport to the analysis lab as specified in the SRM.

OT: off-treatment; the first off-treatment visit occurs 7 days after the last study treatment dose received, whether planned or last dose given after participant is withdrawn from study treatment (e.g., the planned first off-treatment visit occurs on Day 169, 7 days after the Day 162 visit; if participant is withdrawn from study treatment on Day 50, the first off-treatment visit occurs on Day 57)

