7. DISCONTINUATION OF STUDY INTERVENTION AND PARTICIPANT DISCONTINUATION/WITHDRAWAL

7.1. Discontinuation of Study Intervention

A participant may withdraw from the study treatment at any time at his/her own request or may be withdrawn at any time at the discretion of the Investigator for safety, behavioural or administrative reasons. Participants that are discontinued from treatment will enter the post-treatment period unless consent is withdrawn. Every effort should be made to complete the early termination (ET) study procedures and observations if the participant does not enter post-treatment follow-up.

Any laboratory parameter that meets the stopping criteria should be repeated to confirm the value prior to withdrawal

In rare instances, it may be necessary for a participant to permanently discontinue (definitive discontinuation) study intervention. If study intervention is definitively discontinued, the participant may remain in the study to be evaluated for safety and efficacy assessments. For participants meeting the stopping criteria (Section 7.1.1-Section 7.1.4), participants should be monitored until laboratory abnormalities resolve, stabilize, or return to within baseline values as indicated. The participant must then attend the follow-up visits specified in the SoA. See the SoA for data to be collected at the time of discontinuation of study intervention and follow-up and for any further evaluations that need to be completed.

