4.3. Secondary Endpoint(s) Analyses

4.3.1. Key secondary endpoint(s)

4.3.1.1. Efficacy of GSK3228836 on biomarkers and virus-specific antibody response

The group of estimands supporting the secondary objective of assessing the efficacy of GSK3228836 on biomarkers and virus-specific antibody responses for each sub-population are the population summary for each variable in each treatment arm 1-4.

Missing data for variables defined above (except for Time to ALT normalization) will be ignored, only available data will be summarized. No sensitivity analysis is planned for the group of estimands supporting this objective.

Estimands supporting this objective are defined as follows:

- **Population**: one subpopulation of participants with CHB on stable nucleos(t)ide therapy and a second subpopulation of participants with CHB not currently on nucleos(t)ide therapy. For the time to ALT normalization endpoint, only subjects with ALT>ULN at baseline will be included. For summaries of HBe antibody (anti-HBeAg) levels, only participants who are HBeAg Positive at baseline will be included.
- Treatments: arms 1-4. Estimation within each arm.
- Intercurrent events: For the proportion of participants achieving HBsAg <LLOQ and HBV DNA <LLOQ in the absence of rescue medication at the end of treatment analysis window, end of treatment will be determined using the end of treatment analysis window defined in Section 4.2.2. In line with the primary endpoint, missing data not due to wide disruptive events will be imputed as non-response. Missing data due to wide disruptive events will be ignored without any imputation.

Other endpoints will be summarized regardless of completing IP, interruptions in IP or adherence to IP (treatment policy strategy) and regardless of rescue medication (except

for ALT normalization which can only be achieved in the absence of rescue medication). HBV DNA, HBsAg, HBeAg levels that are below the LLOQ will be imputed for summaries of actual values and change from baseline following the rules in Section 4.1.1.

1) Categorical Variables:

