- Achieving HBsAg <LLOQ and HBV DNA <LLOQ at the end of treatment analysis window. Data will be presented overall and by baseline stratification factors (HBsAg <3 log IU/mL and Negative HBeAg; BsAg >3 log IU/mL and Negative HBeAg; HBsAg <3 log IU/mL and Positive HBeAg; HBsAg >3 log IU/mL and Positive HBeAg; HBsAg <3 log IU/mL and All HBeAg; All HBsAg and Negative HBeAg; HBsAg <3 log IU/mL and All HBeAg; All HBsAg and Positive HBeAg)
- Categorical changes from baseline in HBsAg (e.g., <0.5, ≥0.5, ≥1, ≥1.5, ≥3 log₁₀ IU/mL) and in HBV DNA (e.g., <1, ≥1, ≥2, ≥3 log IU/mL). Change from baseline will be presented at each visit and for the following time periods: up to and including Week 6, Up to and including Week 12, Up to and including Week 24, Up to and including off-treatment Week 24. Data will be presented overall and by baseline stratification factors (HBsAg <3 log IU/mL and Negative HBeAg; BsAg >3 log IU/mL and Negative HBeAg; HBsAg >3 log IU/mL and Positive HBeAg; HBsAg >3 log IU/mL and All HBeAg; All HBsAg and Negative HBeAg; HBsAg <3 log IU/mL and All HBeAg; All HBsAg and Positive HBeAg)
- ALT normalization (ALT \leq ULN) over time in absence of rescue medication in participants with baseline ALT \rightarrow ULN
- HBe antibody (anti-HBeAg) levels in HBeAg Positive patients
- HBs antibody (anti-HBsAg) levels (HBs Antibody >=11.5 IU/L is HBs antibody positive and HBs Antibody <11.5 IU/L is HBs antibody negative)
- **Population summary:** proportion of participants in each category for each treatment arm.

2) Continuous Variables:

- Actual values and change from baseline over time of HBsAg and HBV DNA
- Actual values and change from baseline of HBeAg levels
- HBs antibody (anti-HBsAg) levels
- **Population summary**: mean values and mean changes from baseline for each variable in each treatment arm.

3) Time to Event Variable:

- Time to ALT normalization in absence of rescue medication in participants with baseline ALT>ULN.
- **Population summary**: Turnbull's estimator for the non-parametric estimation of time to ALT normalization in each treatment arm.

ALT normalization is defined in subjects with ALT>ULN at baseline as a return to ≤ULN (ULN = 40 for males and 33 in females). Time to ALT normalization is defined as time from baseline to the first follow-up where subject's ALT has returned to normal.

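### By-visit secondary summaries are declared treatment policy, but the SAP's visit rules take participants who stop dosing early out of the later on-treatment rows

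*SAP*

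**What the plan says.** SAP 4.3.1.1 sets the strategy for the secondary biomarker endpoints other than end-of-treatment response: "Other endpoints will be summarized regardless of completing IP, interruptions in IP or adherence to IP (treatment policy strategy"). For the categorical HBsAg and HBV DNA endpoints it adds "Change from baseline will be presented at each visit and for the following time periods", the periods being cumulative ones up to Week 6, Week 12, Week 24 and OT-Week 24. The continuous endpoints and ALT normalization are also shown over time. Missing data "will be ignored, only available data will be summarized"; time to ALT normalization is exempt from that rule.

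The time axis is set in SAP 6.2.2: "Planned time relative to dosing will be used in figures, summaries, statistical analyses and calculation of any derived parameters, unless otherwise stated". SAP 6.2.2.1 gives a table of study-day windows for laboratory data, then limits it: "Visit windows are to be used for windowing of Early Termination visits only".

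The protocol says where an early stopper goes. Section 7.1: "Participants that are discontinued from treatment will enter the post-treatment period unless consent is withdrawn". The note under the off-treatment table in section 1.3: "the first off-treatment visit occurs 7 days after the last study treatment dose received", with the example "if participant is withdrawn from study treatment on Day 50, the first off-treatment visit occurs on Day 57". HBsAg, HBV DNA and chemistry are taken at every off-treatment visit, and HBeAg too in those HBeAg positive at screening. SAP 6.2.3 uses the same anchor.

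**The concern.** A treatment-policy summary at Week 24 should contain the Week 24 status of everyone still followed, on drug or off. Under the rules above, someone who stopped dosing at Week 8 and stayed in the study has no further on-treatment visit. They are missing from each later on-treatment row, and the available-data rule drops them without comment. The row then describes those still being dosed, under a label that says otherwise.

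The samples reappear in the OT rows, pooled with completers' samples from quite different study days, so those rows mix time since last dose with time since baseline.

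The rules also treat same-day samples differently. An Early Termination visit on Day 162 is windowed to Week 24. A participant who stopped on Day 50 but stayed in the study, sampled on that same day, is recorded at OT-Week 16. Leaving the study puts the value in the Week 24 row; staying keeps it out.

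Elsewhere the SAP avoids this. The primary endpoint (4.2.2.1) and end-of-treatment response (4.3.1.1) use study-day windows, and 4.6.4 counts from the planned end of treatment and expressly sets visit labels aside.

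**Working it through.** **Inputs.** OT-Days 1, 8, 22, 50, 78, 106, 134 and 162 (protocol 1.3, off-treatment table). Week x falls on Day 1 + 7(x − 1) (SAP 6.2.2.1), so Week 12 is Day 78 and Week 24 is Day 162. Windows of ±3 days for Weeks 5 to 24 (SAP 6.2.2.1). Primary end-of-treatment windows of Days 64-98 for arm 3 and Days 148-182 for arms 1, 2 and 4 (SAP 4.2.2.1). About 66 participants per arm in arms 1 to 3 of each population (SAP 5).

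**Formula.** OT visit study day = last dose day + 7 + (OT-Day − 1).

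**Reproducing the protocol's figures.** Last dose Day 50: 50 + 7 + 0 = 57. Last dose Day 162: 162 + 7 + 0 = 169. Both match the protocol.

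**Full schedules.**

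| OT visit | Last dose Day 50 | Study week of that day | Completer, last dose Day 162 |
|---|---|---|---|
| OT-W1 | 57 | Week 9 | 169 |
| OT-W2 | 64 | Week 10 | 176 |
| OT-W4 | 78 | Week 12 | 190 |
| OT-W8 | 106 | Week 16 | 218 |
| OT-W12 | 134 | Week 20 | 246 |
| OT-W16 | 162 | Week 24 | 274 |
| OT-W20 | 190 | – | 302 |
| OT-W24 | 218 | – | 330 |

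The Day 78 and Day 162 values are missing from the Week 12 and Week 24 rows and are pooled with completers' Day 190 and Day 274 values.

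**How often a usable value exists.** I took each weekly dosing day before the target as the last dose (11 before Day 78, 23 before Day 162), with visits on their nominal days.

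- ±3-day windows: a Week 12 value for 4 of 11 (last dose Days 22, 50, 64, 71), and a Week 24 value for 7 of 23 (Days 22, 50, 78, 106, 134, 148, 155).
- Days 64-98 and 148-182: 11 of 11 and 23 of 23, the nearest value always within 14 days of target.
- Ties occur. Last dose Day 36 gives visits on Days 64 and 92, each 14 days from Day 78, and on Days 148 and 176, each 14 days from Day 162.

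**Scale.** The documents give no discontinuation rate. If 5% to 20% stop before Week 24 (assumed), 66 × 0.05 = 3.3 to 66 × 0.20 = 13.2 participants per arm leave that row.

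**Direction.** With fraction f stopping, reported mean − treatment-policy mean = f × (mean in continuers − mean in stoppers). Take f = 10% and invented log10 HBsAg changes:

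- Stoppers −2.0, continuers −1.0: the treatment-policy mean is 0.9 × (−1.0) + 0.1 × (−2.0) = −1.10, so a reported −1.0 understates the decline by 0.10/1.10 = 9%.
- Stoppers −0.3, continuers −1.5: the treatment-policy mean is 0.9 × (−1.5) + 0.1 × (−0.3) = −1.38, so a reported −1.5 overstates it by 0.12/1.38 = 9%.

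Over f = 5% to 15% the two cases run from 5% to 13% understated and from 4% to 14% overstated. They show only that the sign is open.

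**The case against.** The strongest reply is that this is a matter of labelling in descriptive tables. Regimen selection uses SVR alone. The prominent end-of-treatment endpoint, HBsAg and HBV DNA below LLOQ, has study-day windows with non-responder imputation. Time to ALT normalization runs from baseline. The cumulative categories keep values from before stopping, although the SAP does not say how they treat OT visits. Time since last dose is a legitimate axis, and stoppers' later values are relabelled, not lost. All of this stands and limits the point to the by-visit rows.

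The use of nominal visit labels is also inferred: from the planned-time rule in SAP 6.2.2, the note in 6.2.2.1 and the contrast with 4.6.4. The output specification is not among the documents and might window these visits. If so, the SAP should say so.

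Two stronger readings are tempting, and neither is supported. A reader might infer that every early stopper has a sample on the Week 12 or Week 24 day. Day 50 is a favourable case; most weekly last-dose days leave the nearest sample 7 or 14 days away. A reader might also infer that stopping is mainly driven by ALT flares in responders, so that the bias has a known sign. Protocol section 7.1 lists liver, vascular and complement, platelet and renal rules, as well as participant request and investigator discretion, and describes permanent discontinuation as rare. The protocol's figure of 6 of 8 flare participants with more than a 1 log HBsAg reduction comes from treatment-naïve participants with ALT at least 2 × ULN in an earlier study, not from people who discontinued. Protocol 8.3.7.1 does link therapeutic flares to antiviral effect, so stopping cannot be assumed independent of response, but nothing further follows.

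**Conclusion.** The point holds for the by-visit HBsAg, HBV DNA, HBeAg and ALT-normalization summaries in SAP 4.3.1.1. Followed as written, the rules give something close to an on-treatment summary under a treatment-policy label, treat same-day samples differently for those who leave and those who stay, and mix study days in the OT rows. Stopping after Week 12 affects only the later rows.

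The size and direction of any distortion cannot be stated from the documents. The counts of recoverable visits assume nominal visit and dosing days; the off-treatment visit allowance of up to ±10 days would shift individual cases. Worth correcting because the data are already collected, but no primary or decision-making result depends on it.

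**What to change.** Keep note 2 in SAP 6.2.2.1 and add an exception. For participants who discontinue study treatment early and remain in the study, scheduled post-discontinuation values are assigned by actual study day in the by-visit tables of 4.3.1.1.

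- Week 12 and Week 24 rows, all arms: the value nearest the target day within Days 64-98 and Days 148-182. For ties, take the earlier value, as 4.2.2.1 already does for its post-treatment windows.
- Other weeks and OT rows: the existing 6.2.2.1 table.
- State that one sample may serve two rows. Day 155, for example, fits both Week 23 and the wider Week 24 window.
- Report n in every row, and keep tables by time since last dose as a supplement.

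Deleting note 2 instead would leave it unclear whether completers' laboratory and vital-sign data are re-windowed too, and the ±3-day table alone would recover only 4 of 11 and 7 of 23.

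The cost is a paragraph of SAP text and one programming step, with no new data. The remaining gaps are that some Week 12 and Week 24 values lie up to 14 days from target, and that early stoppers stay absent from some other weeks and from late OT rows. In the Day 50 example the last scheduled visit is Day 218, so nothing is available from OT-Week 12 on.
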